11.1. Statistical Hypotheses

11.1.1. Pooled Phase 3 (Cohort 1) and Phase 2 (Cohort 1A)

The statistical hypotheses are presented in [Table 6](#).

Table 6: Phase 3 Statistical Hypotheses

Type	Null Hypothesis
Primary virologic endpoint	There is no difference in the time weighted average change from baseline viral load in NP sample through day 7 between the REGN10933+REGN10987 2.4g and 8.0g combined dose group and placebo in the Seronegative mFAS population in the pooled phase 3 cohort 1 and phase 2 cohort 1A
Primary clinical endpoint	There is no risk reduction in the REGN10933+REGN10987 2.4g and 8.0g combined dose groups versus placebo in terms of cumulative incidence of death or mechanical ventilation from day 6 to day 29 in the High Viral Load mFAS population in the pooled phase 3 cohort 1 and phase 2 cohort 1A

Type	Null Hypothesis
	There is no risk reduction in the REGN10933+REGN10987 2.4g and 8.0g combined dose groups versus placebo in terms of cumulative incidence of death or mechanical ventilation from day 6 to day 29 in the Seronegative mFAS population in the pooled phase 3 cohort 1 and phase 2 cohort 1A
	There is no risk reduction in the REGN10933+REGN10987 2.4g and 8.0g combined dose groups versus placebo in terms of cumulative incidence of death or mechanical ventilation from day 6 to day 29 in the overall mFAS population in the pooled phase 3 cohort 1 and phase 2 cohort 1A
	There is no risk reduction in the REGN10933+REGN10987 2.4g and 8.0g combined dose groups versus placebo in terms of cumulative incidence of death or mechanical ventilation from day 1 to day 29 in the High Viral Load mFAS population in the pooled phase 3 cohort 1 and phase 2 cohort 1A
	There is no risk reduction in the REGN10933+REGN10987 2.4g and 8.0g combined dose groups versus placebo in terms of cumulative incidence of death or mechanical ventilation from day 1 to day 29 in the Seronegative mFAS population in the pooled phase 3 cohort 1 and phase 2 cohort 1A
	There is no risk reduction in the REGN10933+REGN10987 2.4g and 8.0g combined dose groups versus placebo in terms of cumulative incidence of death or mechanical ventilation from day 1 to day 29 in the overall mFAS population in the pooled phase 3 cohort 1 and phase 2 cohort 1A

11.2. Justification of Sample Size

The initial sample size for this study was estimated separately for phase 1 and phase 2 (ie, prior to protocol amendment 6) and it was based on the original primary endpoint: virologic efficacy endpoint of time-weighted average change from baseline in viral load. The final estimates on sample size were based on assumptions related to the clinical endpoint of death or mechanical ventilation (see Section 11.2.3).

11.2.1. Phase 1 (Sentinel Safety Group; Cohort 1 only)

The sample size for phase 1 is a total of 60 patients randomized in a 1:1:1 allocation ratio to REGN10933+REGN10987 combination therapy 2.4 g IV, REGN10933+REGN10987 combination therapy 8.0 g IV, or placebo, ie, approximately 20 patients per arm across 3 treatment arms, stratified by the background standard-of-care. The sentinel safety group consists of the first 30 patients randomized in the combined phase 1 portions of R10933-10987-COV-2066 and R10933-10987-COV-2067.

Since one of the objectives of phase 1 is to assess safety and tolerability, the sample size will allow preliminary estimation of the incidences of SAE and AESIs in these investigational treatment arms relative to placebo.

The primary efficacy endpoint in phase 1 is the virologic endpoint of time-weighted average change from baseline in viral load (\log_{10} copies/mL) in **NP swab samples** from day 1 to day 22.

Due to lack of data from the literature on the variation of time-weighted average change from baseline in viral load in COVID-19, the standard deviation of actual viral load values at a timepoint from the literature was used for the following calculation. Assuming standard deviation of $2.1 \log_{10}$ copies/mL ([Cao, 2020](#)), a sample size of 20 patients per arm in phase 1 will have at least 80% power to detect a difference of $1.91 \log_{10}$ copies/mL between the treatment arm and placebo group, using a two-sample t-test at a 2-sided significance of $\alpha=0.05$. The smallest treatment difference is approximately $1.34 \log_{10}$ copies/mL.

11.2.2. Phase 2 (Cohort 1A, Cohort 1, Cohort 2*, and Cohort 3*)

** Per IDMC recommendation first received on 30 October 2020, and reiterated through 19 February 2021, patient enrollment in cohort 2 and cohort 3 has been placed on hold.*

The sample size of phase 2 cohort 1A was adjusted to approximate 1000 patients based on clinical judgement without statistical justification. However, this target was not reached because the enrollment was prematurely terminated due to slow enrollment rate.

Phase 2 will evaluate the efficacy and safety of 2 doses of REGN10933+REGN10987 versus placebo within cohort 1A, cohort 1, cohort 2 and cohort 3, ie, phase 2 contains 3 treatment arms each across 4 cohorts. Randomization will be stratified according to Section [8.6](#).

Initial Estimation of Phase 2 Sample Size

The sample size for phase 2 was originally based on the primary virologic endpoint of time-weighted average change from baseline in viral load (\log_{10} copies/mL) from day 1 to day 22, using a 2-sample t-test at a 2-sided significance of $\alpha=0.05$.

Similar to phase 1, the standard deviation of actual viral load values at a timepoint from the literature was used for sample size calculation due to lack of corresponding data from the literature. Assuming a ~23% dropout rate (including missing data at baseline) and a standard deviation of $2.1 \log_{10}$ copies/mL ([Cao, 2020](#)), a sample size of 130 patients per arm (ie, 100 patients per arm with available data) across 3 treatment arms within each of the 4 cohorts, ie, 390 patients per cohort (for a total of 1560 patients in the phase 2 portion of the study) will have 80% power to detect a difference of $0.84 \log_{10}$ copies/mL between each treatment arm and placebo in a cohort. If a standard deviation of $3.8 \log_{10}$ copies/mL is assumed ([Wang, 2020b](#)), the detectable difference at 80% power would be $1.51 \log_{10}$ copies/mL.

Phase 1/2 Estimation of Sample Size

Per protocol amendment 6, statistical power calculations are provided for the cumulative incidence of death or mechanical ventilation for phase 1/2 cohort 1.

For phase 1/2 analysis in cohort 1, assuming a total number of events (death or mechanical ventilation) will be 35, that the cumulative incidence of death or mechanical ventilation in placebo is 25% at day 29 (placebo rate was 12.5% in Sponsor's Kevzara® [sarilumab] study 6R88-COV-2040 in COVID-19 hospitalized randomized and treated patients receiving low flow oxygen supplementation at baseline; further assume placebo rate is twice this in seronegative mFAS), and using a futility threshold of $\alpha=0.3$ (1-sided), the minimum hazard ratio (HR) between REGN10933+REGN10987 dose group versus placebo that excludes futility is 0.827 (ie, minimum risk reduction 17.3%). If the observed risk reduction is approximately 17% or lower, the assessment of efficacy in cohort 1 as currently designed will be declared futile.

The alpha level for futility in this study is consistent with that used in the ACTIV-3 protocol for a similar cohort of patients with COVID-19 ([NIAID, 2020](#)).

For phase 1/2 key secondary analyses in cohort 1, and using assumptions about event rates as described above, about 43 total events in the seronegative mFAS will be needed to achieve 80% power to detect a risk reduction of 50% (HR=0.5) between any REGN-COV2 dose group versus placebo, at $\alpha=0.1$ (one-sided) level of significance. Assuming patients are followed through day 29, and accrual takes 90 days, and assuming that 30% of FAS (randomized and treated) patients are in the seronegative mFAS, a total of approximately 250 randomized and treated patients across 3 arms will be needed in phase 1/2 in the three treatment groups.

Table 7: Statistical Power for Death or Mechanical Ventilation Endpoint: Phase 1/2 Cohort 1

α (Overall Type 1 error)	Power	Cumulative incidence of death or mechanical ventilation in Placebo by Day 29 (assumption)	Hazard Ratio	# of Events needed in seronegative mFAS	Total Sample Size estimated
0.1 (one-sided)	80%	25%	0.5	43	250
0.1 (one-sided)	80%	25%	0.6	78	413
0.1 (one-sided)	90%	25%	0.5	62	360
0.1 (one-sided)	90%	25%	0.6	114	604

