8.6. Method of Treatment Assignment

Patients will be randomized according to a central randomization scheme using an interactive web response system (IWRS).

Phase 1

60 patients will be randomized in a 1:1:1 allocation ratio to 1 of the following:

- Co-administered REGN10933+REGN10987 combination therapy, 2.4 g (1.2 g each of REGN10933 and REGN10987) IV single dose
- Co-administered REGN10933+REGN10987 combination therapy, 8.0 g (4.0 g each of REGN10933 and REGN10987) IV single dose
- Placebo IV single dose

Randomization will be stratified by type of background standard-of-care being administered for COVID-19 at randomization as follows:

- Antiviral therapies (remdesivir or other)

- Non-antiviral therapies (immune-based therapies, both antiviral and immune-based therapies, or no COVID-19-specific treatment)

Phase 2

Note: Per IDMC recommendation first received on 30 October 2020, and reiterated through 19 February 2021, randomization to cohort 2 and cohort 3 has been placed on hold.

For each of the study cohorts in phase 2, patients will be randomized in a 1:1:1 ratio to receive 1 of the treatments below:

- Co-administered REGN10933+REGN10987 combination therapy 2.4 g (1.2 g of REGN10933 plus 1.2 g of REGN10987) IV single dose
- Co-administered REGN10933+REGN10987 combination therapy 8.0 g (4.0 g of REGN10933 plus 4.0 g of REGN10987) IV single dose
- Placebo IV single dose

Randomization will be stratified by country and type of background standard-of-care being administered for COVID-19 at randomization as follows:

- Antiviral therapies (remdesivir or other)
- Non-antiviral therapies (immune-based therapies, both antiviral and immune-based therapies, or no COVID-19-specific treatment)

Phase 3

Patients will be randomized in a 1:1:1 ratio to receive 1 of the treatments below:

- Co-administered REGN10933+REGN10987 combination therapy 2.4 g (1.2 g of REGN10933 plus 1.2 g of REGN10987) IV single dose
- Co-administered REGN10933+REGN10987 combination therapy 8.0 g (4.0 g of REGN10933 plus 4.0 g of REGN10987) IV single dose
- Placebo IV single dose

Randomization will be stratified by country and type of background standard-of-care being administered for COVID-19 at randomization as follows:

- Antiviral therapies (remdesivir or other)
- Non-antiviral therapies (immune-based therapies, both antiviral and immune-based therapies, or no COVID-19-specific treatment)

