2.3. Sample Size and Power Considerations

The initial sample size for this adaptive study, COV-2066, was estimated separately for phase 1 and phase 2 and was based on the original primary virologic endpoint of time-weighted average change from baseline to day 7 in viral load.

In phase 1, a sample size of a total of 60 patients in Cohort 1 as the sentinel safety group was planned per discussions with regulatory authorities, i.e., 20 patients per arm in each of the 3 treatment arms. Since the goal was to assess safety and tolerability of REGN10933+REGN10987, this sample size would allow preliminary estimation of the incidences of SAEs and AESIs.

Cohorts 1A, 2 and 3 were to be enrolled after phase 1, beginning with the phase 2 portion of the study.

For phase 2 portion of the study, an initial sample size of 390 patients per cohort (i.e., 130 patients per arm) in each of cohorts 1A, 1, 2, and 3, for a total of 1560 patients was planned. This sample size was based on 80% power to detect a treatment difference of 0.84 log₁₀ copies/mL for the primary virologic endpoint assuming a standard deviation of 2.1 log₁₀ copies/mL and 23% dropout rate.

Per Protocol Amendment 6, an interim database lock for analysis of phase 1/2 combined data was planned and accordingly phase 2 sample size for Cohort 1 (low flow oxygen) was adapted to reflect the planned futility analysis using the primary clinical endpoint of death or mechanical ventilation. A total of 43 events of death or mechanical ventilation in seronegative modified Full Analysis Set (seronegative mFAS) patients in Cohort 1 was estimated to achieve 80% power to detect a risk reduction of 50% (HR=0.5) between any REGN10933+REGN10987 dose groups (2.4g IV or 8.0g IV) versus placebo at $\alpha=0.1$ (one-sided) level of significance. This translated to a total sample size

of 250 randomized and treated patients across 3 arms, assuming patients would be followed through day 29, accrual takes 90 days, and 30% of FAS (randomized and treated) patients are in the seronegative mFAS.

The sample size of phase 2 cohort 1A was adjusted to approximate 1000 patients based on clinical judgement without statistical justification. However, this target was not reached because the enrollment was prematurely terminated.

Per IDMC recommendation received on 30 October, 18 November, 10 December 2020, patient enrollment in cohort 2 and cohort 3 has been placed on hold based on a potential safety signal.

Phase 3 Sample Size

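### Phase 1/2 event counts: the printed 80% and 90% powers belong to pooled doses versus placebo, but the text assigns the power to any dose group, where it is about 74–75% and 85–86%

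*Protocol*

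**What the plan says.** Protocol 11.2.2, under the phase 1/2 sample size estimate, states that "about 43 total events in the seronegative mFAS will be needed to achieve 80% power" at a hazard ratio of 0.5. The claim is for "80% power to detect a risk reduction of 50% (HR=0.5) between any REGN-COV2 dose group versus placebo", "at $\alpha=0.1$ (one-sided) level of significance", and the section adds that "a total of approximately 250 randomized and treated patients across 3 arms will be needed". Table 7 extends this to four rows of events and sample sizes:

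- 80% power, HR 0.5: 43 events, size 250
- 80% power, HR 0.6: 78 events, size 413
- 90% power, HR 0.5: 62 events, size 360
- 90% power, HR 0.6: 114 events, size 604

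The table does not name a contrast; only the sentence about the first row does. SAP 2.3 repeats the 43-event statement with the contrast given as "between any REGN10933+REGN10987 dose groups (2.4g IV or 8.0g IV) versus placebo". Neither place says that the calculation pools the doses.

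**The concern.** Under 1:1:1 randomization, one dose against placebo is a 1:1 comparison and the two doses together against placebo is a 2:1 comparison. These need different numbers of events. Events in the dose arm that is not being compared also add to a three-arm total without informing the single-dose test. If the counts were derived for the pooled contrast, the printed power is too high for the contrast in the text. Someone reading a null 2.4 g or 8.0 g result would then credit it with more power than it had at those totals. SAP 2.3 also offers this statement as the basis on which the cohort 1 phase 2 size was adapted.

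**Working it through.** **Inputs.** From Protocol 11.2.2 and Table 7: one-sided alpha 0.1 (z = 1.2816), power 80% or 90% (z = 0.8416 or 1.2816), HR 0.5 or 0.6, and the assumption that "the cumulative incidence of death or mechanical ventilation in placebo is 25% at day 29". From Protocol 8.6: "For each of the study cohorts in phase 2, patients will be randomized in a 1:1:1 ratio".

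**Step 1: reproduce the printed counts.** Schoenfeld: d = (z_alpha + z_power)² / [p(1−p)(ln HR)²], where p(1−p) is 2/9 for 2:1 and 1/4 for 1:1. In the first row the numerator is (1.2816 + 0.8416)² = 4.508 and (ln 0.5)² = 0.4805. The 2:1 result is 4.508 / (0.2222 × 0.4805) = 42.2, and the 1:1 result is 4.508 / (0.25 × 0.4805) = 37.5.

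| Row | Printed | 2:1 | 1:1 |
|---|---|---|---|
| 80%, HR 0.5 | 43 | 42.2 | 37.5 |
| 80%, HR 0.6 | 78 | 77.7 | 69.1 |
| 90%, HR 0.5 | 62 | 61.5 | 54.7 |
| 90%, HR 0.6 | 114 | 113.3 | 100.7 |

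Rounded up, 2:1 gives every printed count and 1:1 gives none. Freedman's formula at 1:1 gives 41, 73, 60 and 106, which also match no row.

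**Step 2: are the counts three-arm totals?** Take placebo incidence p0 = 0.25 and active incidence p1 = 1 − 0.75^HR, which is 0.1340 for HR 0.5 and 0.1585 for HR 0.6. Mean incidence over three equal arms is (p0 + 2p1)/3 = 0.1727 or 0.1890. Dividing the printed events by it gives 249.1, 412.6, 359.1 and 603.1, which round up to the printed sizes 250, 413, 360 and 604. So the counts are totals over three arms. (This step does not use the 30% seronegative share. How many randomized patients are needed to yield the events is a separate question.)

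**Step 3: power at those totals.** With both doses at the stated HR, placebo plus one dose holds the share (p0 + p1)/(p0 + 2p1) of the events: 0.7413 for HR 0.5 and 0.7204 for HR 0.6. Single-dose power is Φ(√(d_pair/4) × |ln HR| − 1.2816). In the first row d_pair = 43 × 0.7413 = 31.9, and √(31.9/4) × 0.6931 − 1.2816 = 0.676, so power is 75.0%.

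| Row | Total events | Events in the pair | Pooled power | Single-dose power |
|---|---|---|---|---|
| 80%, HR 0.5 | 43 | 31.9 | 80.5% | 75.0% |
| 80%, HR 0.6 | 78 | 56.2 | 80.1% | 73.7% |
| 90%, HR 0.5 | 62 | 46.0 | 90.2% | 85.7% |
| 90%, HR 0.6 | 114 | 82.1 | 90.1% | 84.9% |

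A log-rank simulation at the Table 7 sizes (exponential times, follow-up to day 29, 20,000 runs per row) gave single-dose power of 73.8%, 73.2%, 85.3% and 84.7%.

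**Step 4: other assumptions.** For the two 80% rows, single-dose power is 72–73% by Freedman's formula, 71–72% if the pair is given two thirds of the events, and about 69% if the other dose has no effect. It would exceed the stated 80% (about 84%) only if all the events fell in the two compared arms, and Step 2 rules that out.

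**The case against.** The strongest reply is that any dose group was meant loosely, as patients on any active dose. Every printed figure is then right and only a clarifying word is missing. There is support for this in Protocol 11.2.2: it speaks of total events and three arms, and Table 7 shows one overall alpha of 0.1 per row with no division between doses. The futility sentence in the same section also refers to a dose group, yet its threshold of 0.827 at 35 events is closer to the pooled calculation (0.829) than to a 1:1 calculation on all 35 events (0.838). This reading may be what was intended. It does not rescue the text, because SAP 2.3 names the groups as 2.4 g or 8.0 g, and SAP 5.6.3 uses the same parenthesis for pairwise comparisons of each dose with placebo.

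The reply is also right that little now depends on the statement:

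- The phase 1/2 data were locked on 22 December 2020.
- Phases 1 and 2 randomized 60 + 629 = 689 cohort 1 patients, not 250.
- The final hierarchy (Protocol 11.4.9, SAP 5.6.3) tests only the combined doses, in patients who were not part of that lock. Single-dose comparisons there are descriptive.
- Protocol 11.2.2 itself assumes 35 events for the futility assessment. At 35 events even the pooled contrast has about 74% power at HR 0.5: √(35 × 2/9) × 0.6931 − 1.2816 = 0.65. The 43-event row is therefore a planning scenario.

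A reader might go further and infer that formal single-dose tests were run with an inflated type II error. The documents do not support this: the key secondary tests were governed by the phase 1/2 SAP of 21 December 2020, which is not among them, and neither supplied document specifies a formal single-dose test at one-sided 0.1.

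**Conclusion.** The statement is wrong as written. The counts and the printed powers fit pooled doses against placebo, while the text names any dose group. The overstatement for a single dose is about 5 and 6 percentage points in the 80% rows (75.0% and 73.7%) and about 4 and 5 points in the 90% rows (85.7% and 84.9%). These figures rest on the plan's 25% placebo incidence, one-sided alpha 0.1, equal arms, proportional hazards and both doses at the stated HR. If the other dose did less, the shortfall would be larger.

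Two wider inferences should be resisted. Power near 75% does not apply to all four counts: it belongs to the 43- and 78-event rows only. Nor do the figures show that the trial needed more events or patients, because for the pooled contrast the counts are adequate as printed. What changes is a stated power and the weight given to a null single-dose result.

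**What to change.** In Protocol 11.2.2 (the text and Table 7) and SAP 2.3, state that the event counts and power are for the combined 2.4 g and 8.0 g groups against placebo, with 2:1 allocation. Add a column or sentence giving the single-dose power at the same totals (about 75%, 74%, 86% and 85% in row order), with the assumption that both doses have the stated HR. The cost is a wording change and one column. The stated power for single doses becomes slightly less favourable. No change to enrollment, data or the final primary analysis is needed.

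### The phase 1/2 cohort 1 sample size of 250 is a count of seronegative mFAS patients labelled as randomized and treated patients; the assumed 30% seronegative share was not applied

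*Protocol*

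**What the plan says.** The phase 1/2 power paragraph of Protocol 11.2.2 places the required events in a subset: "about 43 total events in the seronegative mFAS will be needed". The target is 80% power at one-sided alpha 0.1, "to detect a risk reduction of 50% (HR=0.5) between any REGN-COV2 dose group versus placebo". The placebo assumption is that "the cumulative incidence of death or mechanical ventilation in placebo is 25% at day 29". The 25% is twice the 12.5% seen in an earlier sponsor study, and the doubling is made for the seronegative mFAS. The paragraph then assumes day-29 follow-up, 90 days of accrual and a 30% share of FAS patients in the seronegative mFAS, and concludes that "a total of approximately 250 randomized and treated patients across 3 arms will be needed in phase 1/2 in the three treatment groups".

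Table 7 sets event counts in the seronegative mFAS (43, 78, 62, 114) beside estimated total sample sizes (250, 413, 360, 604), without saying which population the totals count.

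SAP 2.3 says that the 43 events translate to a total "of 250 randomized and treated patients across 3 arms, assuming patients would be followed through day 29", and again lists the 30% share among the assumptions.

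For the futility calculation, the same protocol section works from a smaller number, "assuming a total number of events (death or mechanical ventilation) will be 35". Protocol 7.1 reports 60 phase 1 and 629 phase 2 patients randomized in cohort 1.

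**The concern.** The stated inputs cannot give the stated result. If 30% of 250 patients are seronegative, 75 patients would have to supply 43 events, a 57% event rate (43/75). Even if all 75 carried the 25% placebo rate, only about 19 events would occur (75 × 0.25 = 18.75).

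What is at stake is how the phase 1/2 key secondary result is read. Comparing 689 randomized patients with a requirement of 250 suggests 2.8 times the numbers needed (689/250). If the requirement was really about 830, the cohort had about 83% of it (689/830).

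**Working it through.** **Inputs.** From Protocol 11.2.2: one-sided alpha 0.1; power 80% or 90%; HR 0.5 or 0.6; placebo incidence 25% by day 29; 30% seronegative share. From Protocol 6.1.1: 1:1:1 allocation, which is 2:1 if the two doses are combined against placebo.

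**Step 1: reproduce the event counts.** Schoenfeld's formula with a 2:1 split is

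events = (z₀.₉₀ + z_power)² / [(1/3)(2/3)(ln HR)²].

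For 80% power and HR 0.5: (1.2816 + 0.8416)² / [(2/9) × 0.4805] = 42.2, rounded up to 43. The other rows give 77.7, 61.5 and 113.3, rounded up to 78, 62 and 114. All four match Table 7. A 1:1 comparison of one dose with placebo gives 38, 70, 55 and 101, and two-sided alpha 0.1 gives 58, 107, 81 and 148. Neither matches.

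**Step 2: reproduce the totals.** Under proportional hazards the active incidence is 1 − 0.75^HR: 0.134 at HR 0.5 and 0.1585 at HR 0.6. The average over placebo and two active arms is (0.25 + 2 × 0.134)/3 = 0.1726, or (0.25 + 2 × 0.1585)/3 = 0.1890. Dividing the events by this average gives the number of patients at that risk. Those are seronegative mFAS patients, because the 25% rate was set for that population.

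| Power, HR | Events | Events ÷ mean incidence | Table 7 total | ÷ 0.30 |
|---|---|---|---|---|
| 80%, 0.5 | 43 | 249.1 | 250 | about 830 |
| 80%, 0.6 | 78 | 412.6 | 413 | about 1,375 |
| 90%, 0.5 | 62 | 359.1 | 360 | about 1,197 |
| 90%, 0.6 | 114 | 603.1 | 604 | about 2,010 |

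Every Table 7 total is reproduced before the 30% share is used. The last column is the unrounded quotient divided by 0.30. Dividing the rounded table values instead gives 833, 1,377, 1,200 and 2,013, an immaterial difference.

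The same method without a subset share gives 241 events and about 2,499 patients for phase 3 cohort 1, against 241 and 2,505 in Protocol 11.2.3. This supports the diagnosis.

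**Step 3: what 250 randomized and treated patients would give.** 250 × 0.30 = 75 seronegative patients, and 75 × 0.1726 = 12.9 events. Power = Φ(√(12.9 × 2/9) × ln 2 − 1.2816) = 0.46.

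**Step 4: what the patients actually randomized would be projected to give.** 60 + 629 = 689; 689 × 0.30 = 206.7 seronegative patients; 206.7 × 0.1726 = 35.7 events; power about 0.75. At exactly 35 events, Φ(√(35 × 2/9) × ln 2 − 1.2816) = 0.74.

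**Step 5: other readings of the 250.** None makes it a valid FAS count at a 30% share. Open follow-up to the end of the 90 + 29 days needs about 388 FAS patients, a data cut at the end of accrual about 983, and a 50% reduction on the risk scale about 860 (258/0.30). If the power statement means one dose against placebo, 250 FAS patients give about 9.6 events and 42% power, and 43 events would need about 1,120.

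**The case against.** The best defence concerns weight rather than arithmetic, and most of it stands.

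- **The phase is finished.** Patients randomized through 01 December 2020 were analysed after the 22 December 2020 database lock under a separate phase 1/2 SAP. The final primary tests use pooled phase 3 cohort 1 and phase 2 cohort 1A, with their own sample-size statement. No test, alpha level or enrolment decision in the current SAP rests on the 250.
- **A reader might infer that phase 1/2 ran at 46% power.** The documents do not support this. The 46% describes a cohort of 250, and 689 patients were randomized.
- **A reader might take the 35 events assumed for futility as proof of the diagnosis,** since 689 patients project to about 36. The protocol does not say how 35 was obtained, and the match needs HR 0.5. The same 206.7 seronegative patients give about 39 events at HR 0.6 (206.7 × 0.189) and about 52 with no effect (206.7 × 0.25). The data cutoff of 09 December 2020 also left some patients short of day 29. The 35 is consistent with the diagnosis and no more. It does tell a careful reader that fewer than 43 events were expected.
- **A reader might conclude that the analysis actually fell short of its events.** Neither document gives the observed seronegative count or event count, so no actual shortfall is documented.
- **The dose wording is ambiguous.** Any dose group can be read as any active dose, pooled. The phase 1/2 SAP, which would settle this, is not among the documents.

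None of this makes 250 a correct number of randomized and treated patients.

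**Conclusion.** The point holds as an error in the written justification. The 250 is understated by a factor of about 3.3 (830/250) for the 80% power claimed, and the other three Table 7 totals carry the same omission if read as randomized and treated patients. The explicit mislabel is one protocol sentence and its SAP counterpart. The Table 7 column is ambiguous and takes its meaning from that sentence.

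The practical size is modest: a projected 74% to 75% power at HR 0.5 for the cohort as randomized, against the stated 80%. That projection rests on the plan's 30% share, 25% placebo rate and HR 0.5, complete day-29 follow-up, and the combined doses compared with placebo. It should be fixed, because two current documents carry a figure that contradicts its own stated assumption.

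**What to change.** - **Table 7:** relabel the totals as seronegative mFAS patients and add a column of randomized and treated patients at a 30% share: about 830, 1,375, 1,197 and 2,010.
- **Protocol 11.2.2 and SAP 2.3:** correct the sentence giving 250 randomized and treated patients. About 250 is the seronegative mFAS count; about 830 is the corresponding FAS count.
- **Power:** state that the 35 events assumed for futility give about 74% power at HR 0.5 and one-sided alpha 0.1.
- **Comparison:** state that the event counts correspond to the combined doses against placebo at 2:1, and reconcile the any-dose-group wording in both documents with the comparison specified in the phase 1/2 SAP.

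The cost is a few lines of text in two documents and a less favourable stated requirement. No data, analysis or enrolment changes.
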